5.8 Subject Replacement Strategy

Subjects who fail to complete study therapy will not be replaced.

5.9 Clinical Criteria for Early Trial Termination

Early trial termination will be the result of the criteria specified below:

1. Quality or quantity of data recording is inaccurate or incomplete
2. Poor adherence to protocol and regulatory requirements
3. Incidence or severity of adverse drug reaction in this or other studies indicates a potential health hazard to subjects
4. Decision by principal investigator and ad hoc DSMC to terminate the study after a stopping rule has been met.
5. Plans to modify or discontinue the development of the study drug
In the event of Genentech decision to no longer supply study drug, ample notification will be provided so that appropriate adjustments to subject treatment can be made.

6.0 TRIAL FLOW CHART

6.1 Part A Study Flow Chart

Treatment Cycle/Title	Screening Period	Part A					End of Treatment ⁹
		Cycle 1 Day 1	Cycle 1 Day 2	Cycle 1 Day 8	Cycle 1 Day 15	Cycles 2-8 Day 1	
Scheduling Timing and Window	-42 to -1d			± 1 day	± 1 day	± 2 days	± 2 days
Informed Consent	X						
Inclusion/Exclusion Criteria	X						
Medical History	X						
Prior and Concomitant Medication Review	X	X		X	X	X	X
Trial Treatment Administration		X		X	X	X	
Post-study disease status							
Survival Status							
Review Adverse Events ²	X	X		X	X	X	X
Physical Examination	X	X		X	X	X	X
Vital Signs and Weight	X	X		X	X	X	X
Height	X						
ECOG Performance Status	X	X		X	X	X	X
Pregnancy Test – Urine or Serum beta-HCG ¹	X						
PT/INR and aPTT	X						
CBC with Differential ⁸	X	X		X	X	X ¹¹	X
Comprehensive Serum Chemistry Panel ⁸ and LDH	X	X	X ¹¹	X	X	X	X
Uric acid, Phosphate		X	X ¹¹				
HepB S Ag, Core Ab, Hep C and HIV screen	X						

Product: Mosunetuzumab, Polatuzumab vedotin, obinutuzumab
Protocol/Amendment No: v4.2

Treatment Cycle/Title	Screening Period	Part A					End of Treatment ⁹
		Cycle 1 Day 1	Cycle 1 Day 2	Cycle 1 Day 8	Cycle 1 Day 15	Cycles 2-8 Day 1	
Scheduling Timing and Window	-42 to -1d			± 1 day	± 1 day	± 2 days	± 2 days
Tumor Imaging ³	X					X ³	X ³
Bone Marrow Biopsy and Aspirate ⁴	X						X
Other Procedures (Optional) ⁵	X						
Archival Tissue Collection, if Feasible ⁶	X						
Correlative Studies Blood Collection ⁷	X	X					X

Cycle length = 21 days.

1. For women of child-bearing potential only. Should be repeated to ensure a value is also available within 72 hours of C1D1)
2. AE will be recorded from the time of a subject signing consent, up until off study visit.
3. See Section 7.1.2.5: Tumor Imaging: Baseline and post cycle 8 imaging is mandatory. This should consist of a FDG-PET and concurrent diagnostic CT scan of the abdomen and pelvis (if clinically indicated). Baseline imaging must be performed within 42 days of initiating study drug therapy. Post cycle 8 imaging should be performed any time between cycle 9 day 1/end of treatment visit. An interim CT should be performed between Cycle 4 day 1 and cycle 5 day 1 (as close to cycle five day 1 as possible). Additional imaging should be performed at investigator discretion.
4. Screening bone marrow biopsy and aspirate may be completed up to 12 weeks prior to study enrollment, and at time of CR (as close to date of CR as possible). Bone marrow biopsy may be waived at the discretion of the Principal Investigator.
5. See Section 7.1.4. Other procedures during screening are at the discretion of the treating investigator and may include standard-of-care assessments, central venous catheter placement, laboratory studies, or other measures.
6. The presence of archival tissue will be assessed during screening, and unstained slides may be collected. When available this tissue will be provided for central biobanking.
7. Baseline correlative blood draw (eg. For ctDNA measurements) may be done at any time prior to the C1D1 dose. Additional correlative timepoints will be collected at baseline, as well as around the time of any response assessment. Correlative blood draws should also be performed for the end of treatment or off study visit in patients who do not achieve CR at assessment. Additional timepoints may be drawn at the time of other expected blood draws at the discretion of the investigator.
8. See Table 8 for details of these tests.
- 9: End of treatment visit should be scheduled at the time of the expected cycle 9 day 1, or within 14 days of removal from protocol. Subjects who are not in CR and do not proceed with Cycle 9 Day 1 of polatuzumab vedotin and obinutuzumab as outlined in section 5.2 and 6.2.
10. Study-mandated visits are not required, but the study team may query records to assess disease status or vital status for up to 5 years after completion of therapy. Patients on alternative therapy should have AEs recorded for up to 30 days after last dose of study therapy or first administration of alternate therapy, whichever comes first.
11. Monitoring for tumor lysis syndrome should be performed on cycle 1 day 2. Liver function testing is optional. Additional supportive care and monitoring can be provided as determined by baseline testing and risk factors.

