Subjects who must permanently discontinue mosunetuzumab monotherapy due to toxicity should have a response assessment with positron emission tomography (PET)/CT as soon as is clinically feasible and be evaluated for consideration of treatment in Part B as outlined below. These subjects would then be realigned to cycle 9 day 1 provided at least 21 days \pm 2 days have passed since the last mosunetuzumab injection

Subjects will undergo a computed tomography (CT) between cycle 4 day 1 and cycle 5 day 1. Those with at least stable disease (SD) or better by Lugano²³ criteria will proceed with treatment for cycles 5-8. Subjects with progressive disease (PD) at this timepoint may proceed with cycles 5-8 if the investigator assesses that the subject is deriving clinical benefit from the study medication (e.g. pseudoprogression). If there is no clinical benefit to this medication seen in patients with PD, subjects should receive additional therapy outside of the protocol.

Imaging with a PET/CT will be performed between cycle 8 day 1 and cycle 9 day 1. Subjects in a complete remission (CR) will not receive any further study therapy and will be observed in long term follow up. For this response assessment, a Deauville score will be assigned by the clinical radiology read. If the sub-investigator or principal investigator disagrees with the Deauville score assigned, another nuclear medicine physician will adjudicate the results.

All other subjects who do not achieve a CR may proceed with Part B of study treatment. Those with progressive disease (PD) may proceed with Part B only if they are deriving clinical benefit from the treatment (e.g., pseudoprogression, mixed response overall reduction in tumor) after discussion with the Principal Investigator.

Mosunetuzumab Dose Modifications/Toxicity Management

Administration of mosunetuzumab will be performed in a clinical setting with immediate access to a code team staff who are trained to monitor for and respond to medical emergencies. Additional management may take place after transfer to the University of Washington Medical Center, where there is access to neurology and nephrology consultation services in the event of cytokine release syndrome and tumor lysis syndrome, respectively.

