- For neutropenia, the ANC should resolve to Grade ≤ 2 or return to $\geq 80\%$ of the baseline value, whichever is lower.
- For increased lab values the abnormality should have resolved to the upper limit of Grade ≤ 1 , or return to $\leq 120\%$ of the baseline value, whichever is higher.

In the event that a patient has a toxicity in Cycle 1 necessitating mosunetuzumab interruption for >7 days, the Principal Investigator should be notified and the patient may be required to repeat mosunetuzumab at the highest dose previously tolerated prior to resuming the planned treatment schedule.

If scheduled dosing coincides with a holiday that precludes dosing, dosing should commence on the nearest following date, with subsequent dosing continuing on a 21-day schedule as applicable.

Patients who discontinue all study treatment for adverse events should continue to have disease assessments per institutional standard of care.

Additional guidance on the management of other risks that may be associated with mosunetuzumab is described in Appendix 14.9 (Neurologic AEs), Appendix 14.10 (Tumor Inflammation or flare), Appendix 14.11 (Neutropenia and thrombocytopenia), Appendix 14.12 (Infections) and Appendix 14.13 (Elevated Liver Enzymes).

Part B

For patients eligible for treatment in Part B, treatment will commence with cycle 9 day 1. This may be delayed for patients who require a washout of an agent listed in appendix 14.4. Cycle length is 21 days. Polatuzumab vedotin will be administered on day 1 of each cycle. Obinutuzumab 1000 mg will be administered (See table 5 and 6 for details on pre-medications and infusion related reaction management) on cycle 9 day 1, day 8, and day 15. From cycle 10 onwards obinutuzumab will only be administered on day 1 (1000 mg). Part B will be administered for 6 total cycles (through cycle 14). A response assessment by CT should be performed after cycle 11, and an end of treatment PET/CT should be performed after cycle 14. Obinutuzumab should be administered prior to polatuzumab vedotin on days that both drugs are administered.

Table 3: Part B dosing table

	Cycle 9			Cycle 10-14
	Day 1	Day 8	Day 15	Day 1
Obinutuzumab IV	1000 mg	1000 mg	1000 mg	1000 mg
Polatuzumab vedotin IV	1.8 mg/kg			1.8 mg/kg

Cycle length = 21 days

Dose Modification

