5.6.2 Contraception

The study agents may have adverse effects on a fetus in utero. Furthermore, it is not known if the study agents have transient adverse effects on the composition of sperm.

Women of childbearing potential must agree to remain abstinent (refrain from heterosexual intercourse) or use contraceptive methods that result in a failure rate of < 1% per year during the treatment period and for at least 12 months after the last dose of study treatment. Women must refrain from donating eggs during this same period. A woman is considered to be of childbearing potential if she is post-menarcheal, has not reached a postmenopausal state (≥ 12 continuous months of amenorrhea with no identified cause other than menopause), and has not undergone surgical sterilization (removal of ovaries and/or uterus). The definition of childbearing potential may be adapted for alignment with local guidelines or requirements. Examples of contraceptive methods with a failure rate of < 1% per year include bilateral tubal ligation, male sterilization, hormonal contraceptives that inhibit ovulation, hormone-releasing intrauterine devices, and copper intrauterine devices.

The reliability of sexual abstinence should be evaluated in relation to the duration of the clinical trial and the preferred and usual lifestyle of the patient. Periodic abstinence (e.g., calendar, ovulation, symptothermal, or post-ovulation methods) and withdrawal are not acceptable methods of contraception.

Men must agree to remain abstinent (refrain from heterosexual intercourse) or use a condom, and agree to refrain from donating sperm, as defined below: With female partners of childbearing potential or pregnant female partners, men must remain abstinent or use a condom during the treatment period and for at least 5 months after the last dose of polatuzumab vedotin. Men must refrain from donating sperm during this same period.

The reliability of sexual abstinence should be evaluated in relation to the duration of the clinical trial and the preferred and usual lifestyle of the patient. Periodic abstinence (e.g., calendar, ovulation, symptothermal, or postovulation methods) and withdrawal are not acceptable methods of preventing drug exposure. Male patients considering preservation of fertility should bank sperm before study treatment.

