6.2 Part B Study Flow Chart

Treatment Cycle/Title	Part B					
	Cycle 9 Day 1	Cycle 9 Day 2	Cycle 9 Day 8	Cycle 9 Day 15	Cycles 10-14 Day 1	
Scheduling Timing and Window			± 1 day	± 1 day	± 2 days	
Prior and Concomitant Medication Review	X		X	X	X	
Trial Treatment Administration	X		X	X	X	
Post-study disease status						
Survival Status						
Review Adverse Events ¹	X		X	X	X	
Physical Examination	X		X	X	X	
Vital Signs and Weight	X		X	X	X	
Height						
ECOG Performance Status	X		X	X	X	
CBC with Differential ⁵	X		X	X	X ¹¹	
Comprehensive Serum Chemistry Panel ⁵ and LDH	X	X ⁷	X	X	X	
Uric acid, Phosphate	X	X ⁷				
Tumor Imaging ²					X ²	
Bone Marrow Biopsy and Aspirate ³						
Correlative Studies Blood Collection ⁴	X					

Cycle length = 21 days

1. AE will be recorded from the time of a subject signing consent, up until off study visit.
2. A CT scan should be performed between cycle 11 day 1 and cycle 12 day 1 (as close to cycle 12 day 1 as possible). Post cycle 14 PET/CT (with concurrent diagnostic CT scan of the chest, abdomen, and pelvis (neck if clinically indicated)). Additional interim and surveillance scans can be performed at investigator discretion.
3. Screening bone marrow biopsy and aspirate may be completed up to 12 weeks prior to study enrollment, and at time of CR (if positive at enrollment or of not performed to date of CR as possible). Bone marrow requirements may be waived at the discretion of the Principal Investigator.
4. Baseline correlative blood draw (eg. For ctDNA measurements) should be done at any time prior to the C9D1 dose, preferably at the time other C9D1 labs have been collected. Additional timepoints will be collected with day 1 labs prior to cycle 10, 11, as well as around the time of any response assessment. Correlative blood draws should also be performed at the off study visit in patients who did not have a formal response assessment. Additional timepoints may be drawn at the time of other expected blood draws at the discretion of the investigator.
5. See Table 8 for details of these tests.

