7.1.2.5 Tumor Imaging and Assessment of Disease

Tumor imaging consists of standard of care imaging at baseline during the screening period, including FDG-PET/CT with contrast-enhanced computed tomography (CT) of the chest, abdomen, and pelvis.

For measurement of response, 2014 criteria as described in “Recommendations for Initial Evaluation, Staging, and Response Assessment of Hodgkin and Non-Hodgkin Lymphoma: The Lugano Classification” will be used (see Appendix 14.3).²³

- **Baseline imaging** must be performed prior to initiating study drug therapy as outlined in the study calendar including PET/CT and diagnostic quality CT. Additional baseline imaging may be performed as indicated for standard of care and clinical purposes including MRI, or CT imaging of the neck.
- **Interim imaging** should be performed prior to Cycle 5, 9, and 12 as outlined in sections 6.1 and 6.2. Imaging prior to cycle 9 should be a PET/CT with concurrent diagnostic CT, while other interim imaging assessments can be a diagnostic CT alone unless additional imaging is clinically necessary.
- **Off study:** For patients only completing part A, the post cycle 8 scan will serve as the off study imaging. For patients participating in part B, end of treatment tumor imaging performed should be performed after cycle 14 day 1 and as close to the end of study visit (4-6 weeks, +/-7 days after cycle 14 day 1) as possible. Imaging should include PET/CT with diagnostic quality CT.

All CT scans should be performed with IV contrast unless contraindicated, and abdominal and pelvis scans should be performed with oral contrast.

All CT and FDG-PET/CT scans are to be interpreted locally; central review of radiology will not be performed. For response assessments with a PET/CT, the clinical read and images will be reviewed by the investigator, and if there are disagreements, a third person (radiologist) will adjudicate.

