7.1.3.1 Laboratory Safety Evaluations (Hematology, Chemistry)

Laboratory tests for hematology, chemistry, and others are specified in Table 8 below. HBV Surface Antigen (Hep B S Ag), HBV Core Antibody (Hep B Core Ab), HIV screening, Hep C Ab screening will be performed during the screening period, and reviewed and managed at the study site as per clinical standard of care.

Table 8: Laboratory Tests

Hematology	Chemistry	Urinalysis	Other
Hematocrit	Albumin	Urine pregnancy test †	Serum β -human chorionic gonadotropin (β -hCG)†
Hemoglobin	Alkaline phosphatase		
Platelet count	Alanine aminotransferase (ALT)		PT (INR)
WBC (total and differential)	Aspartate aminotransferase (AST)		aPTT
Red Blood Cell Count	Lactate dehydrogenase (LDH)		
	Carbon Dioxide, (CO_2 or bicarbonate)‡		
	Calcium		
	Chloride		Blood for correlative studies
	Glucose		HBV Surface Antigen, HBV Core Ab, HIV screen, Hep C Ab screening
	Potassium		
	Sodium		
	Total Bilirubin		
	Total protein		
	Blood Urea Nitrogen		
† Perform on women of childbearing potential only. If urine pregnancy results cannot be confirmed as negative, a serum pregnancy test will be required.			
‡ If considered standard of care in your region.			

After Cycle 1, pre-dose laboratory procedures can be conducted up to 72 hours prior to dosing. Results must be reviewed by the investigator or qualified designee and found to be acceptable prior to each dose of trial treatment.

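### No pregnancy test is required before the first polatuzumab vedotin and obinutuzumab doses at Cycle 9 Day 1

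*Combined protocol and SAP*

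**What the plan says.** Scheduled pregnancy testing appears in two places. Inclusion criterion 10 (section 5.1) requires a negative serum test in the screening period. Chart 6.1 marks the test in the screening column only, and its footnote 1 adds: "Should be repeated to ensure a value is also available within 72 hours of C1D1". Table 8 (section 7.1.3.1) lists the urine and serum tests but gives no time point.

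Chart 6.2, which governs Part B, has a Cycle 9 Day 1 column but no pregnancy-test row, and none of its footnotes mentions one. The Part B treatment text (section 5.3) and the visit text (sections 7.1.6.2 and 7.1.6.3) do not ask for a test either.

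On fetal risk, section 5.6.2 states: "The study agents may have adverse effects on a fetus in utero". Section 5.6.3 removes a subject who becomes pregnant on treatment, and section 5.7 stops therapy after a confirmed positive serum test. Neither schedules a test.

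The start of Part B can move. For subjects who stop mosunetuzumab for toxicity and have been reassessed, section 5.3 says: "These subjects would then be realigned to cycle 9 day 1". Of Cycle 9 Day 1 it says: "This may be delayed for patients who require a washout of an agent listed in appendix 14.4".

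**The concern.** The protocol looks for pregnancy just before first exposure to the Part A drug, but not just before first exposure to the two Part B drugs. One of these, polatuzumab vedotin, delivers a microtubule inhibitor (section 4.2). Part B runs for up to six cycles.

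A recent, unsuspected pregnancy at Cycle 9 Day 1 could therefore be exposed to both new agents. The removal rules in 5.6.3 and 5.7 need the pregnancy to be known, and nothing in the Part B schedule is designed to make it known. What is at stake is fetal safety; the statistical design is untouched.

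**Working it through.** **Age of the last required test at Cycle 9 Day 1**

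- Nominal interval from C1D1 to C9D1: 8 cycles × 21 days = 168 days. A test taken up to 72 hours before C1D1 is 168 to 171 days old at the first Part B dose.
- Earliest realignment after toxicity: section 5.3 requires 21 ± 2 days since the last mosunetuzumab injection, so 21 − 2 = 19 days if that injection was on C1D1.
- Washout or dose delays: longer than 168 days, with no upper limit stated for the washout.

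**Existing controls, and whether any of them requires a test**

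| Control | Where | Requires a test before Part B? |
|---|---|---|
| Contraception failing in under 1% per year | 5.6.2 | No; lowers risk, does not detect failure |
| Exclusion of women intending pregnancy | 5.2, item 21 | No |
| Visits with physical examination | 6.1, 6.2 | No |
| PET/CT before Cycle 9 | 5.3, 7.1.2.5 | No; a response assessment |
| Unscheduled testing | 7.1 | No; discretionary |
| Removal or discontinuation | 5.6.3, 5.7 | No; acts on a known pregnancy |

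The imaging is the control most likely to show an established pregnancy. Section 7.1.2.5 says: "Imaging prior to cycle 9 should be a PET/CT with concurrent diagnostic CT". Its timing is loose, however: "Imaging with a PET/CT will be performed between cycle 8 day 1 and cycle 9 day 1". It can thus precede the first Part B dose by up to 21 days nominally, and by more if a washout follows.

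**Probability of conception**

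No figure in the plan bears on this, so there is nothing to reproduce. Taking the 1% per year ceiling as a constant rate, the probability over d days is 1 − 0.99^(d/365).

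| Period | d | Probability per woman |
|---|---|---|
| Whole of Part A | 168 | 0.46% |
| Last 12 weeks (assumed unnoticed) | 84 | 0.23% |
| Last 8 weeks (assumed unnoticed) | 56 | 0.15% |
| Last 4 weeks (assumed unnoticed) | 28 | 0.08% |
| Longest nominal gap from PET/CT to C9D1 | 21 | 0.06% |
| Earliest toxicity realignment | 19 | 0.05% |

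The first row is an upper bound for unnoticed pregnancy, because one conceived early in Part A would probably be recognised at a visit or on the PET/CT. The 4, 8 and 12 week rows are assumptions; the documents give no basis for choosing among them.

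**The case against.** The best defence is that the protocol follows a coherent model: test at entry, require contraception throughout, and remove anyone who becomes pregnant. Section 7.1.6.2 treats Parts A and B as one treatment period, and other screening-only tests (coagulation, hepatitis, HIV) are not repeated in chart 6.2 either. The omission may well be deliberate. That is a fair reading, but it does not explain why first exposure to mosunetuzumab needs a fresh result and first exposure to two other agents does not.

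A pregnancy conceived during Part A has probably already met mosunetuzumab. This stands: a test at Cycle 9 Day 1 would not keep the fetus free of study drug. It would still prevent up to six cycles of two further agents.

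The existing controls are wider than section 5.7 alone. Section 5.6.3 applies however a pregnancy is recognised, a subject may report symptoms, section 5.6.2 keeps out women whose contraceptive compliance is in doubt, and under section 7.1 the manufacturer as well as the investigator may ask for extra safety testing. These narrow the gap, but none requires a test when pregnancy is not suspected.

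The numbers are small. Even if all 42 subjects were women of childbearing potential and all entered Part B, the 8-week assumption gives 42 × 0.00154 = 0.06 unnoticed pregnancies, and the upper bound gives 42 × 0.00462 = 0.19. The true figure is lower, since complete responders stop after Part A. This stands too, and limits the point to a cheap safety improvement.

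Finally, footnote 1 asks only that a value be available; it does not say negative or bar dosing. The wording proposed below is stricter. It applies to Part B what inclusion criterion 10 (a negative result) and section 5.7 (stop on a confirmed positive) already require.

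**Conclusion.** The concern holds. No section requires a pregnancy test tied to the start of Part B, and on the nominal schedule two new drugs are started on a result about 168 days old. The omission cannot be put down to a damaged table, because the Cycle 9 Day 1 column of chart 6.2 is present and neither a row nor a footnote mentions the test.

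The probability is low. The figures assume contraceptive failure exactly at the 1% ceiling and at a constant rate; better contraception would lower them and poor adherence would raise them. The documents do not say how many women of childbearing potential will reach Part B, so no expected count can be given. The sponsor should make the change because the harm is serious and avoidable at very little cost, although the trial's validity does not depend on it.

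**What to change.** Carry the pregnancy-test row of chart 6.1 (urine or serum beta-HCG, women of childbearing potential only) into chart 6.2, with an X at Cycle 9 Day 1. Attach a footnote to this effect: *a negative result must be on file within 72 hours before the actual first Part B dose, and Part B is not started if a positive result is confirmed by serum (section 5.7).*

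Tying the window to the actual dosing date covers both subjects realigned early after toxicity and subjects delayed by washout. The window already exists for other pre-dose laboratory work in section 7.1.3.1: "After Cycle 1, pre-dose laboratory procedures can be conducted up to 72 hours prior to dosing". Blood is taken at this visit anyway; the correlative sample in chart 6.2 is to be drawn "preferably at the time other C9D1 labs have been collected". First exposure to new drugs is the reason for choosing this time point, and no other needs to be added on that ground.

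The cost is one row, one footnote and one laboratory test per woman of childbearing potential entering Part B. No visit is added and no analysis changes.
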